5.6 Data Analysis

[figure not shown]
Sample Size Justification: Below is a diagram of the expected subject recruitment and attrition (see Figure 2). Our recruitment estimates are based on our experience with prior trials (e.g., a recent pilot study of a web based intervention successfully recruited over 90% of potential participants) and our emphasis in the budget of recruitment personnel who will be embedded in our clinics. We conservatively estimate that 60% of potential participants will agree to participate and be successfully enrolled in the study. Our attrition estimate of 20% is based on our experience with an internet self-help intervention study, during which drop out was less than 20%. This was accomplished through continued outreach by the recruiter via letter and calls. Based on these conservative numbers and a recruiting period of 33 months we expect a minimum N=388 participants in the study [(20 newly identified participants per month over 33 months + 150 existing) *60% participation* (1-20% attrition)]. This is a conservative estimate

because we have excluded the existing 1,332 potential participants living in our area (national dataset) to whom we will mail letters.

For each regression model proposed for H1&2, results of sample size calculation using the application PASS v11 (Hintze, 2011) show that a much smaller N=148 (or N=194) achieves 80% (or 90%) power to detect an additional R-Squared of 0.05 (proportion of explained variation in the outcome) attributed to 2 independent variables (TBI Coach plus an interaction) using an F-Test with alpha of 0.05. This assumed the variables tested are adjusted for 10 independent variables with an R-Squared of 0.20.

We note that of all statistical models proposed in this study, the mediation model has the most stringent sample size requirement. With conservative total N=388, we expect to have greater than .80 power to detect a small to medium effect size of the mediated effect at alpha = 0.05. The two regression coefficients (beta1 & beta2) that jointly capture the mediated effects are critical in the power calculation for a mediation

Figure 2. Expected Total Recruitment

model. Using the parameter values of 0.14, 0.39, and 0.59, corresponding to Cohen's criteria68 for small (2% of the variance), medium (13% of the variance), and large (26% of the variance) effect sizes, respectively, Fritz and MacKinnon (2007) conducted empirical estimates of sample

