sizes needed for .8 power at 95% confidence level. Their results showed that when bias-corrected bootstrap is used, N=462 is adequate to detect small effect size for each of alpha and beta while N=377 is adequate to detect small/medium effect size combination for both alpha and beta.69 Conservatively we expect to recruit N=388. We calculated directly the power for testing mediation effect based on Sobel's test (Sobel, 1982) using the R package 'power Mediation'. By specifying Cohen's small ES for each coefficient in the indirect pathway (beta1 = beta2 = 0.14) and with the following assumptions: both the predictor and the mediator have S.D. of 0.5 while the square of the correlation between both equal 0.3; and S.D. of the random error term is 0.2; the expected N=388 will provide 0.82 power to detect the small mediation effect size.

Sample Size for Qualitative Research Questions: In qualitative research, sample size relies on the quality and richness of information obtained. A chieving conceptual saturation is the goal of qualitative research and is not dependent on sample size but on the ability of the data to support interpretations, i.e. saturation. For this aim, we project saturation will occur within the first twelve interviews; meta-themes will present in six interviews. Thus we will recruit 10% of Veterans to provide adequate data to represent sub-groups that may emerge from the sample and allow for an adequate sub-sample sizes; allowing for some attrition. For example, we expect low volume and high volume users; those who intend to have continued use and those who may not. This will also allow sampling groups for analysis by socio-demographics such as gender and race. We have budgeted to recruit 10% of Veteran participants to conduct the proposed interviews.

Data Analysis:

Data from the Concussion Coach application will be electronically sent to the USF server. It will be de-identified (but matched to a study number that will identify the individual to the study coordinator who will need it for follow-up). It will be periodically emailed to study personnel at the Tampa VA.

Data from paper questionnaires will be obtained from the recruiter and study personnel and maintained by the study coordinator. Again, study numbers will be used to identify participants.

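### The 0.82 power stated for a small mediated effect at N=388 (Hypothesis 3) rests on inputs that contradict each other; with consistent inputs and no covariates, Sobel's test cannot exceed 0.795

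*Combined protocol and SAP*

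**What the plan says.** Section 5.6, Sample Size Justification, states that "the mediation model has the most stringent sample size requirement" among the study's models. It then makes two power claims for the mediated effect at N=388, a figure already net of 20% attrition.

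- A general claim of "greater than .80 power to detect a small to medium effect size of the mediated effect", at alpha 0.05.
- A direct calculation with Sobel's test in an R package, concluding that "the expected N=388 will provide 0.82 power to detect the small mediation effect size".

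The inputs to the second claim are Cohen's "small ES for each coefficient in the indirect pathway (beta1 = beta2 = 0.14"), that "both the predictor and the mediator have S.D. of 0.5 while the square of the correlation between both equal 0.3", and that the "S.D. of the random error term is 0.2". The values 0.14, 0.39 and 0.59 are tied to "small (2% of the variance), medium (13% of the variance), and large (26% of the variance) effect sizes". The same paragraph reports published results that, with a bias-corrected bootstrap, "N=462 is adequate to detect small effect size for each of alpha and beta" at 0.8 power, and that 377 suffices for a small/medium combination.

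The analysis text for Hypothesis 3 says that the product of the two path coefficients is not normally distributed and that this affects the power calculation. It plans Bayesian estimation, with inference from posterior percentiles.

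**The concern.** In Sobel's formula, the first coefficient is the slope of the mediator on randomised group. Given the two standard deviations, that slope fixes the group-mediator correlation, so the correlation cannot be chosen separately. The plan enters a small slope and a very large correlation for the same path. The paragraph also sits badly with its own citation: if small/small needs 462 by a bootstrap method, 0.82 at 388 by Sobel's test needs explaining.

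What is at stake is how Hypothesis 3 will be read. A null result could be taken as coming from a test with over 80% power for a small mediated effect, when such an effect had a substantial chance of being missed.

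**Working it through.** **Inputs** (section 5.6): b1 = b2 = 0.14; SDx = SDm = 0.5; r² = 0.3; error SD s = 0.2; n = 388; alpha 0.05. Sidedness is not stated; two-sided is assumed. An SDx of 0.5 corresponds to 1:1 allocation.

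**Formula.** Var(b1) = SDm²(1 − r²)/(n·SDx²) and Var(b2) = s²/(n·SDm²(1 − r²)). With z1 = b1/SE(b1) and z2 = b2/SE(b2), Sobel's z = z1·z2/√(z1² + z2²). Power ≈ Φ(z − 1.96).

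**1. The plan's figure.** z1 = 0.14·√(388/0.7) = 3.296; z2 = 5.768; z = 2.862; power 0.816. The stated 0.82 reproduces.

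**2. The contradiction.** r = b1·SDx/SDm = 0.14 × 0.5/0.5 = 0.14, so r² = 0.0196. An r² of 0.3 with these SDs needs b1 = √0.3 = 0.55. The plan's scale is √(share/(1 − share)): 2%, 13% and 26% give 0.143, 0.387 and 0.593. A share of 30% gives 0.655, beyond large.

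**3. Correct r² only.** z1 = 0.14·√(388/0.9804) = 2.785; z2 = 6.826; z = 2.579; power 0.732. Simulating Sobel's test gives about 0.77. By the formula, 0.80 needs about 458 completers and 0.82 about 483.

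**4. Ceiling.** Because 1/z² = 1/z1² + 1/z2², Sobel's z is always below z1. At z1 = 2.785 the power is 0.795, so no b2 or error SD reaches 0.82 without covariates. The first path alone needs ((1.96 + 0.915)/0.14)² × 0.9804 = 413.6, i.e. 414 completers, for 0.82. Entering r² = 0.3 lifts that path's power to 0.909.

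**5. Other ways to reconcile the inputs.** Keeping r² = 0.3 and b1 = 0.14 requires SDm = 0.128: z = 1.465, power 0.31. Keeping r² = 0.3 and the SDs requires b1 = 0.548: z = 5.265, power above 0.99, but that path is no longer small.

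**6. Second path.** Its share of the outcome variance remaining after group is b2²·SDm²(1 − r²)/(that + s²).
- r² = 0.3: 0.00343/0.04343 = 7.9%, or 0.29 on the plan's scale.
- r² = 0.0196: 0.00480/0.04480 = 10.7%, or 0.35.

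Both are nearer medium (0.39) than small (0.14). With an illustrative error SD of 0.5, which makes this path roughly 2%, the formula gives z = 1.950 and power 0.496.

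**7. Small/small power at N=388, simulated.** These runs used 8,000 to 10,000 trials per case (Monte Carlo error about 0.005), complete data, and 10 covariates where adjusted. The interval is the 2.5 and 97.5 percentiles of the product of flat-prior, normal-approximation posteriors, not the planned software's MCMC.

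| Setting | Power |
|---|---|
| Percentile interval, no covariates | 0.58–0.62 |
| Outcome R² 0.20, mediator R² 0 or 0.20; small as share of residual variance | about 0.57 |
| Same R²; small as share of total variance | 0.63–0.74 |
| Outcome R² 0.50 (assumption), mediator R² 0.40; residual share | about 0.57 |
| Outcome R² 0.50 (assumption), mediator R² 0 to 0.40; total share | 0.74–0.93 |
| Sobel's test, no covariates | 0.37–0.42 |

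A bias-corrected bootstrap (1,500 trials, error 0.012, no covariates) gave 0.70 to 0.72 at 388 and 0.79 at 462, in line with the cited 462.

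**8. What checks out.** Small/medium power at 388 is 0.78 to 0.80 with the percentile interval and 0.805 with the bootstrap. The sizing for Hypotheses 1 and 2 reproduces: 0.801 at 148 and 0.902 at 194.

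**The case against.** The formula was evaluated correctly; the fault lies in the inputs. That is so, but the stated power is still one the design does not have for the effect named.

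Sidedness is not given, and a one-sided test with r² = 0.0196 yields 0.825. This does not rescue the calculation: one-sided with the stated r² = 0.3 gives 0.888, so the plan's 0.82 was two-sided.

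The strongest point is that the planned analysis is neither Sobel's test nor unadjusted. Correcting only r² and keeping the error SD of 0.2, the percentile interval has simulated power of 0.793, about 0.03 below the claim. With covariates explaining 20% of mediator variance as well, it is 0.876. Even 5% lifts the first-path ceiling to 0.816. These figures stand as arithmetic, and the ceiling does depend on having no covariates. But they keep an error SD that makes the second path about 11% of variance, so they do not describe a small/small effect. The power calculation also names no covariates, and it labels the 0.3 as the predictor-mediator correlation squared.

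Using Sobel's test is conservative and does not itself inflate power; this too stands. So does the limited consequence: mediation is exploratory under Aim 2, and the primary hypothesis is untouched.

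**Conclusion.** The concern holds. The 0.82 depends on a squared correlation of 0.3 that contradicts the slope of 0.14 in the same calculation. Making the two agree, with both SDs at 0.5, no covariates and a two-sided 0.05 test, gives 0.73 by the plan's formula, with an absolute ceiling of 0.795.

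On the plan's definition of small (2% per path), the planned type of interval has power of about 0.6 without covariates. At the covariate R-squared of 0.20 that the plan uses for Hypotheses 1 and 2, it is 0.57 to 0.74. Exceeding 0.80 requires stronger covariates than the plan states, and small defined as a share of total variance. The simulated figures assume complete data and approximate the posterior; the contradiction and the ceiling follow from algebra alone. The separate small-to-medium claim is about met. This should be fixed, but it bears only on how Hypothesis 3 is interpreted.

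**What to change.** Delete the 0.82 claim for a small mediated effect. Restate Hypothesis 3 power for the posterior-percentile interval with inputs that fit together: when the two SDs are equal, the squared correlation must equal the squared slope. State whether small means a share of total or residual variance, and give the covariate R-squared assumed for mediator and outcome. Suggested wording, which the sponsor should confirm in the planned software:

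> Assuming complete data on N=388, no covariates, and small = 2% of variance on each path, the 95% posterior-percentile interval has power of about 0.6 for a small/small mediated effect and about 0.80 for small/medium. With covariate R-squared of 0.20, as assumed for H1 and H2, small/small power is about 0.57 if small is a share of residual variance and about 0.63 to 0.74 if it is a share of total variance.

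Claim 0.80 for small/small only if a larger covariate R-squared is justified and stated. Reword the general small-to-medium claim as about 0.80.

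The cost is one reworded paragraph and a less favourable stated power for Hypothesis 3. Enrolment, the primary analysis and the sizing for Hypotheses 1 and 2 are unchanged.

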The VA's Concussion Coach is an interactive, self-management tool designed to address the modifiable 'causes' of PCS identified in our theoretical model. Investigating the utility of the Concussion Coach smart phone application for increased self-management and PCS reduction is the primary focus of this study. Concussion Coach, which is described in the Methods section, is based on an evidence-based review of the PCS intervention literature but delivers it via an innovative, interactive, self-management platform. Randomized controlled trials have demonstrated the effectiveness of a self-management approach to chronic disease in improving self-efficacy, physical and psychological health, and reducing health care utilization in patients with arthritis, lung disease, stroke, heart disease, and multiple sclerosis. We found no studies that applied a chronic disease self-management approach for treating PCS, though such an approach is clearly applicable given the longstanding presence of symptoms and multifactorial contributing predictors (many of which are potentially malleable), as outlined in our model above.

Interactive, computer-based patient education programs have demonstrated utility in a variety of different medical conditions.³ They draw on constructivist learning theories that highlight the importance of active self-paced learning. In a recent review, interactive computer-based patient education programs were found to be as effective or more effective than education provided by healthcare professionals in 7 of 8 studies³ in terms of various clinical outcomes, satisfaction, knowledge gain, and cost savings. Theories of self-management rely on social cognitive theory that posits behavior is influenced by personal factors, environmental factors, and behavior itself.^{50 51} Key personal factors include self-efficacy (or confidence in one's ability), outcome expectancies, and mood. Beliefs that people have about themselves are key elements in the exercise of control and personal agency; individuals are viewed both as products and as producers of their own environments and of their social systems. Improved self-efficacy, expectancy effects, and improved mood, have all been linked to improved health outcomes across many different patient groups. We will attempt to answer the following research questions:

Q1: Is Concussion Coach effective in improving PCS and psychological distress in those with a history of mild TBI?

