3.0 Objectives

The proposed study is a 4-year randomized control trial investigating the utility of an interactive, self-management smartphone application, "Concussion Coach," one of a suite of mobile applications developed by VA. The primary goal of the proposed study is to evaluate the efficacy of Concussion Coach for improving clinical outcomes in those with a history of mild traumatic brain injury (mild TBI) and to determine what aspects of Concussion Coach are most

useful to Veterans. An overarching goal of this line of research is to improve access among Veterans with mild TBI who still have symptoms months to years after injury.

Aim 1. Evaluate the efficacy of Concussion Coach for improving clinical outcomes among recipients of Concussion Coach.

Hypothesis 1 (Primary Hypothesis): Patients randomized to receive Concussion Coach for 3 months will have (a) lower Post-Concussion Symptom severity (PCS) and, (b) lower psychological distress, compared to patients randomized to a no intervention control group, after adjusting for baseline severity and other potential confounders.

Aim 2. Explore mediation/moderation of Concussion Coach effects on clinical outcomes among recipients of Concussion Coach.

Hypothesis 2: The effects of Concussion Coach on PCS (and psychological distress) will be greater for Veterans who have (a) greater comfort with technology at baseline than for those who are less comfortable; (b) greater social support at baseline than for those with less social support.

Aim 3. Determine the aspects of Concussion Coach most associated with positive outcomes.

Hypothesis 3: If Concussion Coach improves Veterans' (a) knowledge about TBI and attribution of symptoms and/or (b) self-efficacy in coping with symptoms, Veterans will have less PCS and psychological distress.

Aim 4. Obtain qualitative information on factors associated with use of Concussion Coach or with deriving benefit from use of Concussion Coach that can be used to inform future modifications of the application and wide scale implementation.

Hypothesis 4: More time spent on (a) Concussion Coach use, and (b) specific interactive components of Concussion Coach (i.e., the "tools" section) will be associated with lower PCS symptom severity after adjusting for baseline PCS values and potential confounders.

Research Question 1: What barriers prevent patients from using the Concussion Coach and from improving on PCS symptom severity?

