- Neurobehavioral Symptom Inventory (NSI) is a 22-item questionnaire developed to evaluate post-concussion symptoms following mild TBI.⁵² It is used throughout the VA system of care to assess complaints associated with identified concussion. Patients are asked to rate each symptom on a scale of 0-4 (none, mild, moderate, severe, and very severe) with three different types of symptoms: affective/psychological/stress, somatic/physical, and cognitive reflecting three factors. The total score will be used in primary analyses. It is our primary outcome of interest because the civilian literature on interventions for mild TBI has focused (and found effects) on symptom-based measures.^{41 53} Our own pilot data suggests that educational interventions have a significant impact on this measure.
- mBIAS is a 5-item measure of atypical symptoms. It is associated with symptom exaggeration following mild TBI (Cooper et al., 2011).
- Brief Symptom Inventory 18 (BSI 18) is a self-report measure with 18 items designed to measure psychological distress. It can be completed in approximately 4 minutes and is well-suited for helping measure symptom change due to treatment. It has good psychometric properties and has been used in the population of interest. It measures three primary dimensions: Somatization, Depression, and Anxiety, as well as a Global Severity Index (GSI). The GSI will be used in primary analyses as a measure of overall psychological distress. The Posttraumatic Stress Disorder Checklist (PCL-5) is a 20-item, self-rating scale that provides a quick and accurate measure of PTSD symptoms. Each item corresponds to current diagnostic criteria of PTSD, and each symptom is rated in terms of frequency and severity (Weathers, Huska, & Keane, 1991).Participant use of Concussion Coach will be collected electronically, including total time spent using the app as well as each component.

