All data will be combined into a study database. The integrity of the database will be managed by our database manager. Analyses will be conducted by the statistician ([name]) and the PI ([name]).

Data Analysis Plan: An intention-to-treat (ITT) analysis will be performed, that is analysis will be based on the groups to which participants are randomized regardless of whether they receive or adhere to the assigned intervention. This will allow us to test the effects of assigning TBI Coach in practice, separate from assessing effects of adherence and/or loss to follow-up. Those who are lost to follow-up and therefore are missing outcome measures (T2 assessments) will be included in separate comparison analyses that utilize multiple imputations of the missing data.

For each primary outcome and other measures consisting of multiple items, a summation score will be produced for each subject. Summary of each variable by intervention group will be cross-tabulated. The time spent on TBI Coach and its specific components on the average will also be tabulated. All primary outcomes will be analyzed as continuous variables. Exploratory bivariate plots will be used to investigate possible nonlinear relationships between baseline/covariates and each follow up outcome variable. In separate statistical models proposed, we will control for demographics and other covariates including the baseline values of the outcome under investigation. Where appropriate, nonlinear regression model will be utilized (e.g., generalized additive model).

Hypothesis 1 (Primary Hypothesis): Patients randomized to receive TBI Coach for 3 months will have (a) lower post-concussive symptom severity and (b) lower psychological distress, compared to patients randomized to a no intervention control group, after adjusting for baseline severity and other potential confounders.

Analysis: The two intervention groups (TBI Coach = 1; Control = 0) will be compared on each outcome (a) and (b) in separate regression models that include the group variable and control for the outcome at baseline and other potential confounders. A significant positive estimated coefficient of the group variable will indicate positive TBI Coach's effects on the outcome, with the standardized value of the coefficient as the standardized effect size.

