Hypothesis 2: The effects of TBI Coach on PCS (and psychological distress) will be greater for Veterans who have (a) greater comfort with technology at baseline than for those who are less comfortable; (b) greater social support at baseline than for those with less social support.

Analysis: Two separate tests of moderated effects of TBI Coach will be performed with respect to each outcome. Each regression model in H1 (one per outcome) will be extended by adding a 2-way interaction term (between intervention and (a) eHealth Literacy Scale and (b) Social Support score; one at a time (i.e. two different moderation models per outcome). A significant coefficient of an interaction term will indicate presence of interactive effects. A co-plot using model fitted values will also be produced to further investigate the nature of any significant interaction.

Hypothesis 3: If TBI Coach improves Veterans' (a) knowledge about TBI and attribution of symptoms and/or (b) self-efficacy in coping with symptoms, Veterans will have less PCS and Psychological Distress.

Analysis: Single-mediator models⁷³ will test the indirect effects of the group variable (TBI Coach) on each outcome (separately) with respect to mediating variables: (a) knowledge and attribution, and (b) self-efficacy. Preliminary regression analyses will test whether (1) TBI Coach substantially changes the mediating variable, and (2) the mediating variable changes the outcome. Next, we will proceed to a full mediation model with simultaneous estimation of both direct and indirect effects of TBI Coach on the outcome. The mediated effect will be estimated as a product of the two path coefficients alpha and beta in the indirect pathway. The distribution of the product of coefficients is non-normal and this has implications for statistical inference as well as power calculation (see section on sample size justification). Therefore, the analysis will

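### The Primary Hypothesis reads a positive group coefficient as benefit although lower scores are better, and no rule says how its two outcomes combine

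*Combined protocol and SAP*

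**What the plan says.** **Hypothesis.** Section 3.0 states that app users will have "a) lower Post-Concussion Symptom severity (PCS) and, (b) lower psychological distress" than controls. Section 5.6 repeats this.

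**Decision rule.** Under Hypothesis 1 in section 5.6, the arms are "compared on each outcome (a) and (b) in separate regression models". Each model adjusts for the baseline value, with app = 1 and control = 0. A significant coefficient with a positive sign is to be read as a favourable effect on that outcome.

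**Direction of the scales.** Section 5.5 has NSI respondents "rate each symptom on a scale of 0-4 (none, mild, moderate, severe, and very severe", and items are summed, so a higher total is worse. Under Hypothesis 4, section 5.6 looks for a negative coefficient of app time on symptom severity.

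**Standing of the outcomes.** Of the NSI, section 5.5 says "It is our primary outcome of interest because the civilian literature on interventions for mild TBI has focused". Of the BSI-18 it says "The GSI will be used in primary analyses as a measure of overall psychological distress". Table 1 puts the PCL-5 beside the BSI in its primary-outcome block.

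**Alpha.** It appears in the sample-size text of section 5.6: "For each regression model proposed for H1&2", an F-test at 0.05. No section gives a testing order, an alpha split or a both-required rule.

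**The concern.** There are two defects in the same rule.

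The first is the sign. Taken literally, the stated criterion for benefit is met when app users end with more symptoms than controls, and it is not met when they end with fewer.

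The second is the missing link between two test results and one hypothesis. The text allows at least three readings:

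1. **Both outcomes must succeed.** Hypothesis 1 joins its parts with *and*, whereas Hypothesis 3 uses a looser connective: "knowledge about TBI and attribution of symptoms and/or (b) self-efficacy in coping with symptoms".
2. **The NSI alone decides.** Section 5.5 singles it out, and the Introduction says that "self-management and PCS reduction is the primary focus of this study".
3. **Either may succeed.** Both measures are assigned to primary analyses, and each model is read on its own.

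The same data could confirm the Primary Hypothesis under one reading and fail it under another. Nothing in the plan stops the choice from being made after the results are seen.

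**Working it through.** **Sign.** With app = 1 and control = 0, the group coefficient is the adjusted mean in the app arm minus that in the control arm. Hypothesis 1 predicts a lower score in the app arm, so the coefficient under benefit is below zero. The rule asks for one above zero. No reverse scoring is stated, and the modelled outcome is the follow-up score with baseline as covariate, not an improvement score.

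**The plan's own figure.** Inputs from section 5.6: added R-squared 0.05 from 2 variables, 10 covariates with R-squared 0.20, alpha 0.05. The F-test has 2 and N − 13 degrees of freedom and noncentrality λ = N × 0.05 / (1 − 0.20 − 0.05). Power is 0.801 at N=148 and 0.902 at N=194, so both stated figures reproduce.

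**False claims of benefit.** Assume no effect on either outcome and two-sided 0.05 per model. The analysis text gives no sidedness; I take it from the F-test, which is non-directional. The documents give no NSI–GSI correlation ρ, so a range is shown. Let (Z1, Z2) be bivariate normal with correlation ρ, larger values favouring the app:

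- either outcome, benefit direction: 1 − P(Z1 < 1.96, Z2 < 1.96)
- either outcome, any direction: 1 − P(|Z1| < 1.96, |Z2| < 1.96)
- both outcomes, benefit direction: P(Z1 > 1.96, Z2 > 1.96)

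| ρ | Either, benefit | Either, any direction | Both, benefit |
|---|---|---|---|
| 0 | 4.94% | 9.75% | 0.06% |
| 0.5 | 4.54% | 9.07% | 0.46% |
| 0.7 | 4.17% | 8.35% | 0.83% |
| 0.8 | 3.90% | 7.81% | 1.10% |
| 0.9 | 3.52% | 7.04% | 1.48% |

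For the NSI alone the figures are 2.5% for benefit and 5% in any direction. The both-required rule never exceeds 2.5%, even when one outcome has a true effect. The Introduction reports that depression and anxiety correlate strongly with post-concussion symptoms, so the lower rows are the plausible ones.

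**Sample size for power.** Section 5.6 expects (20 × 33 + 150) × 0.6 × 0.8 = 388.8, stated as 388. The Abstract reports 419 enrolled as 93% of goal: 419 / 0.93 ≈ 450, and 450 × 0.8 = 360. Both are used.

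**Power with the NSI tested first.** The Hypothesis 1 group test has 1 degree of freedom and λ = N × ΔR² / (0.80 − ΔR²). Power for the GSI behind the gate is the chance that both tests succeed: P(Z1 > 1.96, Z2 > 1.96) with both means equal to √λ. An added R-squared of 0.02 is my assumption; 0.05 is the plan's figure.

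| N | ΔR², both outcomes | λ | GSI ungated | GSI gated, ρ = 0.5 | GSI gated, ρ = 0.9 |
|---|---|---|---|---|---|
| 388 | 0.05 | 25.87 | 0.999 | 0.998 | 0.999 |
| 388 | 0.02 | 9.95 | 0.88 | 0.81 | 0.85 |
| 360 | 0.05 | 24.00 | 0.998 | 0.997 | 0.998 |
| 360 | 0.02 | 9.23 | 0.86 | 0.77 | 0.82 |

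**Uneven effects.** At N=388, assume 0.01 on the NSI and 0.02 on the GSI. Gated GSI power is then 0.57 to 0.60 (ρ 0.5 to 0.9). Holm's procedure rejects the GSI if Z2 > 2.241, or if Z2 > 1.96 and Z1 > 2.241, and treats the NSI likewise. It gives the GSI 0.84 to 0.82 and the NSI 0.58 to 0.60 over the same range.

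**The case against.** The strongest reply is that the text leans towards the readings without inflation. Hypothesis 1 says *and*, the NSI is singled out as the outcome of interest, and no section says that either outcome may carry the hypothesis. The remark that primary outcomes are analysed as continuous concerns variable type, not decision-making. A further reading is possible: two outcome-specific claims, each at its own 5%, with no joint claim. All of this stands, and it is why the inflation is only conditional. It does not close the gap: the *and* is never turned into a success criterion, the preference for the NSI carries no testing order, and two separate claims would still sit under one Primary Hypothesis with no rule for when it is confirmed.

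It is also fair to say that 4.9% needs zero correlation, which the Introduction makes implausible, and that the sign is a drafting slip separate from multiplicity. I agree with both, but the slip is in the stated decision rule, and any success rule needs a correct direction.

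Three stronger inferences are tempting, and the documents do not support them:

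- *The trial as designed has an inflated error rate.* That follows only if either outcome may carry the hypothesis, which is not stated.
- *Outcomes by arm have been or will be examined early.* The Communication Plan only says that site staff would be told of any interim results. No interim analysis by arm is planned.
- *The PCL-5 is a third primary test.* Table 1 leaves its standing open, but section 5.5 names the GSI as the distress measure for primary analyses.

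**Conclusion.** The stated direction is wrong and should be corrected. The error is in the reading rule, not in the model: the estimates do not change, and the documents do not suggest that harm would knowingly be reported as benefit.

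The missing combination rule is a real gap of moderate size. If the NSI alone decides or both outcomes are required, there is no inflation. If either may carry the hypothesis, the chance of a false claim of benefit rises from 2.5% to between 3.5% and 4.2%, an excess of about 1.0 to 1.7 percentage points. In any direction it rises from 5% to between 7.0% and about 8.3%. These figures assume two-sided testing at 0.05, no effect on either outcome, a correlation of 0.7 to 0.9, and no PCL-5 test. The correlation is an assumption.

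**What to change.** **In section 5.6, Hypothesis 1:** state that benefit is a significant negative group coefficient, that is, a lower score in the app arm.

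**In sections 3.0 and 5.6, before any look at outcomes by arm, add:**

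> NSI total at T2 is tested first at two-sided 0.05. BSI-18 GSI at T2 is tested at two-sided 0.05 only if the NSI result is significant in the direction of benefit; otherwise the GSI result is supportive. The PCL-5 is supportive.

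This follows the plan's own preference for the NSI and holds the chance of a false claim of benefit at 2.5% or less. If the team wants equal standing, Holm's procedure across NSI and GSI does the same, counting only results in the direction of benefit: the smaller p-value is judged at two-sided 0.025 and, if it passes, the other at 0.05.

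**Cost.** A wording change and no new data. Under the gate, a significant GSI without a significant NSI is supportive only. The loss of GSI power is negligible at the plan's own effect size, modest if both effects are smaller, and substantial only if the NSI effect is clearly the weaker of the two; in that case Holm is the better choice. Timing matters because 419 patients are already enrolled and the principal investigator is one of the analysts: the rule carries weight only if it is fixed before results by arm are seen.
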